# 6.7 Sleep, Fatigue and Quality of Life Measures

Actigraphy, will be collected annually as described in Section 2.4. Symptom Distress, Multidimensional Fatigue Standard Version, Epworth Sleepiness Scale and Peds Brain Tumor QoL Generic Version and Peds QoL Generic Version will be administered at baseline and every 3 months for the first 2 years, then every 6 months to month 60. During radiation the Multidimensional Fatigue Acute, Symptom Distress, and Brain Tumor QoL and Peds QoL Acute version (measuring QoL over the last 7 days) will be administered weekly. Parental proxy will be obtained as indicated or if patient is unable to complete the questionnaires.

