of metastatic disease at the time of enrollment. Patient must be > 3 years of age. For patients enrolled before August 30, 2019 Test will not be collected after July 1, 2020 \*\*Optional at the dicretion of the treating physician

Table 6.0.3 Evaluations during Radiation Therapy at St. Jude

Frahration		Week on therapy										
Evaluation	1	2	3	4	5	6	7					
Imaging												
Activation PET*	Х	Х	Χ	Χ	Χ	Χ	Χ					
Clinical-Standard												
Physical examination	Х	Х	Χ	Х	Χ	Х	Х					
CBC			Х									
Chemistry			Х									
Clinical-Investigational												
QOL			Χ			Х						
Toxicity Assessment	Х	Х	Χ	Х	Х	Х	Χ					
Laboratory-Investigational												
Cytokines 			Χ			Х						

\*frequency depending on feasibility and availability

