# 11.3 Statistical Analysis of Secondary Objective 1.2.2 Sleep, Fatigue and Quality of Life

Objective: Using specific measures of sleep quality, excessive daytime sleepiness, daytime activity, fatigue, symptom distress, and quality of life, explore associations of sleep, fatigue and quality of life with other measures of CNS effects, clinical and treatment factors in children and young adults with ependymoma treated with a second course of irradiation.

Stratified by treatment arms (focal vs. craniospinal radiation), descriptive statistics of the longitudinal assessments of sleep, fatigue and quality of life will be described. Specifically, on a yearly basis starting from the pre-treatment time point to year 5 post treatment initiation, quality of life in patients  $\geq 2$  years of age as measured by the PedsQoL brain tumor module will be reported; daytime activity and up to 20 sleep measurements as measured by wrist actigraphy along with sleep diary-patient/parent will be reported. On a more frequent basis (every 3 months for the first 2 years, every 6 month to month 60), sleep complaints in patients  $\geq 8$  years of age as measured by Symptom Distress Scale (SDS) and Epworth Sleepiness Scale will be reported and fatigue in patients  $\geq 2$  years of age as measured by The Peds QL Multidimensional Fatigue scale will be reported, along with PedsQoL brain tumor module. The Acute version of the Multidimensional Fatigue scale and Peds brain tumor module will be administered weekly during radiation therapy.

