As an exploratory analysis, each of above mentioned measurements will be compared between two treatment arms by longitudinal data analysis. Generalized Estimating Equation (GEE) will be employed to compare outcome changes over time between two treatment arms by using time and treatment as covariates of the model. The interaction term between treatment arm and time will be added if two arms show different change rate. The other covariates of interest will be selected by Bayesian information criterion (BIC). However, any response with <3 assessments would not be included in the list. To analyze sleep measurements which will be examined annually, the other measurements used in the model will only include their data points measured at the same time as sleep measurements. Multidimensional Fatigue scale and Peds brain tumor module will be measured each week for 4 weeks at the first year. We will analyze them in two ways. First, we will only use the first 4 weeks data to fit the GEE. Second, it will also be fitted in a large time picture but only the first week data of these 4 weeks will be used. In addition, Epworth Sleepiness Scale score will also be dichotomized by 10 and then fitted using GEE with a logistic link.

Similarly, the same modeling approach will be used to explore associations between each of above mentioned outcome and patient characteristics/clinical

St. Jude Children's Research Hospital

IRB NUMBER: Pro00004349
IRB APPROVAL DATE: 02/01/2023

factors that are of interest. The independent effect of resultant significant factors will be explored further in multiple regression models.

Based on the number of tests performed to address this secondary objective, adjustments for multiple comparisons will be made to mitigate over interpreting exploratory findings.

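### The on-treatment fatigue and quality-of-life model in Section 11.3 assumes four weekly assessments, which matches neither weekly collection throughout radiation nor the weeks 3 and 6 in Table 6.0.3

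*Combined protocol and SAP*

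**What the plan says.** The on-treatment schedule for the acute fatigue and quality-of-life questionnaires is given in three ways.

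- **Four weeks.** Section 11.3, in the paragraph on longitudinal modelling, says that the fatigue scale and the brain tumor module "will be measured each week for 4 weeks at the first year". Two analyses follow. For the on-treatment model: "First, we will only use the first 4 weeks data to fit the GEE". For the longer-term model, "only the first week data of these 4 weeks will be used". The GEE compares the focal and craniospinal arms "by using time and treatment as covariates of the model", with an interaction added if the arms change at different rates.
- **Every week of radiation.** Section 6.7 says that the acute versions ("measuring QoL over the last 7 days) will be administered weekly") are given during radiation, with no limit on the number of weeks. The preceding paragraph of 11.3 says the same of the acute fatigue scale and the brain tumor module. Appendix III lists the questionnaires for each week of treatment, both before and under Amendment 2.0.
- **Weeks 3 and 6.** "Table 6.0.3 Evaluations during Radiation Therapy at St. Jude" has columns for weeks 1 to 7 and marks its QOL row at weeks 3 and 6 only. The Appendix II copy is the same. Neither has a separate fatigue row.

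The age limits also differ. Section 11.3 reports "sleep complaints in patients" aged 8 or more, by the Symptom Distress and Epworth scales. Section 6.7 has both scales completed from age 7, and adds an Epworth parent proxy at ages 4 to 6.

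**The concern.** An analysis plan has to describe the data that will exist. Here the number of assessments that the model expects is not the number that either collection plan produces. If the weekly plan is followed, the model leaves out the last weeks of treatment, which have been collected at some burden to children and parents. If the schedule table is followed, the model as specified has too few time points for the effect it is meant to estimate.

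An analyst would then have to choose the weeks after the data are in, which is what a written plan should prevent. What is at stake is the on-treatment part of secondary objective 1.2.2. The age mismatch is a smaller fault of the same kind: some reports are collected for which the plan states no analysis.

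**Working it through.** No power or alpha figure is involved. The check counts assessments and then asks what the specified model can estimate from them.

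**Inputs.** Section 5.9.2 gives one fraction per day at 180 cGy. Its total doses run from 5040 to 5940 cGy, with 5400 cGy in 30 fractions for the main course. Five fractions per week is an assumption; the documents do not state it.

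**Length of treatment.** Fractions = total dose / 180; weeks = fractions / 5, rounded up.

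- 5040 / 180 = 28 fractions; 28 / 5 = 5.6, so 6 weeks.
- 5400 / 180 = 30 fractions; 30 / 5 = 6.0, so 6 weeks.
- 5940 / 180 = 33 fractions; 33 / 5 = 6.6, so 7 weeks.

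**The plan's figure.** Section 11.3 has 4 assessments, in weeks 1 to 4. Weekly collection gives 6 or 7. Table 6.0.3 gives 2. The figure of 4 is not reproduced by either.

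**If collection is weekly.**

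- Share discarded: (6 − 4) / 6 = 2/6 = 33%, or (7 − 4) / 7 = 3/7 = 43%.
- Precision of a linear slope: its variance is proportional to 1/Sxx, where Sxx is the sum of squared deviations of the assessment weeks from their mean. Weeks 1 to 4 give 5.0, weeks 1 to 6 give 17.5 and weeks 1 to 7 give 28.0. The four-week slope variance is therefore 17.5 / 5.0 = 3.5 to 28.0 / 5.0 = 5.6 times that from all weeks. This assumes a linear trend, equal and exchangeable errors and no missing data.
- The cut falls unevenly on the craniospinal arm. Section 5.9.2 gives 20 to 22 neuraxis fractions, which is 4.0 to 4.4 weeks at five per week, and Section 5.9.5 says that the neuraxis phase generally comes first. The first four weeks then leave out most or all of the boost phase in that arm.

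**If Table 6.0.3 is followed.** Only week 3 lies in weeks 1 to 4. The design columns are intercept, time t, arm, and t × arm. With t = 3 in every row, the time column is 3 × intercept and the interaction column is 3 × arm. The rank is 2 of 3 columns, or 2 of 4 with the interaction. With weeks 1 to 4 the rank is full (3 of 3, 4 of 4). So under the table neither the time effect nor the arm-by-time effect can be estimated. The longer-term model keeps its follow-up data but has no week-1 value to include.

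**Adding baseline** does not clearly rescue the first model. Section 6.7 gives the standard or generic versions at baseline and the acute versions during radiation, so the two points would come from different forms.

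**Age.** Age-7 self-reports on both scales, and Epworth proxy reports at ages 4 to 6, are collected but fall below the age limit in 11.3. The number of patients concerned cannot be worked out, because the documents give no age distribution for this trial.

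**The case against.** The strongest reply is that the weekly schedule is by far the better supported. It stands in Section 6.7, in 11.3 itself and in both parts of Appendix III, and only Table 6.0.3 and its copy differ. On that reading the four-week GEE can be fitted. This stands: the failure to estimate the time terms is conditional on the table, and even then an arm comparison at week 3 could be made. The loss of 2 of 6 to 3 of 7 weekly assessments remains.

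It is also fair that the table's row says QOL and not fatigue. Applying weeks 3 and 6 to the fatigue scale is an inference. If the row does not cover fatigue, the table schedules no on-treatment fatigue assessment at all.

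Different practice between sites does not explain the conflict. Table 6.0.3 is headed for St. Jude, and a footnote in Appendix III says that these questionnaires are done only there.

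On age, the limit of 8 stands in a sentence about descriptive reporting. But the next paragraph takes the measurements just listed into the comparison of arms and gives no other limit.

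Two stronger readings are tempting and are not supported.

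- A reader might infer that 11.3's own rule, "any response with <3 assessments would not be included in the list", removes these outcomes under Table 6.0.3, since two is fewer than three. The rule follows a sentence on selecting covariates, speaks of a response and not of a patient, and names no on-treatment window. Counted over the whole study, these measures have 15 scheduled assessments in Table 6.0.2 (baseline; 3, 6, 9, 12, 15, 18, 21, 24; then 30, 36, 42, 48, 54, 60 months).
- A reader might infer that stopping at week 4 misses the peak of fatigue. No place in the documents says when fatigue or quality-of-life effects peak.

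**Conclusion.** The inconsistency is real and lies in current text. The four-week model in 11.3 matches neither collection plan. With weekly collection it discards 33% to 43% of the on-treatment assessments; the lower figure is for 28 to 30 fractions and the upper for 33, both assuming five fractions per week. With Table 6.0.3 it leaves one time point, so the specified time and arm-by-time terms cannot be estimated and the longer-term model lacks its week-1 value. The age limit in 11.3 is one year above the self-report limit in 6.7 for both scales, and the Epworth proxy reports at ages 4 to 6 have no stated analysis.

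The weight of the point is small. Section 11.3 labels the comparison exploratory, it serves secondary objective 1.2.2, and the PFS and OS design is not touched. It is worth correcting because the correction is specific and nearly free.

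**What to change.** - Mark the QOL row of Table 6.0.3 and of its Appendix II copy weekly, in line with Sections 6.7 and 11.3 and Appendix III, and say whether the row includes the fatigue scale.
- In 11.3, replace the four-week restriction with all on-treatment assessments, and define time in the GEE as the actual week of treatment.
- In 11.3, change the age limit for the Symptom Distress and Epworth scales from 8 to 7, and state how the Epworth parent proxy reports at ages 4 to 6 will be handled (for example, described separately or left out of the model).

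The cost is wording in the analysis section and two copies of one table. No new visits are needed if weekly collection is already being done. If practice has followed weeks 3 and 6, the plan should say so and limit the on-treatment analysis to what two assessments can support.

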# 11.4 Statistical Analysis of Secondary Objective 1.2.3 Physical Performance

Objective: To describe physical performance and movement in children, adolescents and young adults with ependymoma treated with a second course of radiation.

Physical performance measures will be obtained at baseline, 12, 24, 36, 48 and 60 months. We will provide descriptive statistics of the following outcomes at each time point, and also provide the plots of individual profiles and mean profiles of the outcomes across time. The descriptive statistical analysis will be stratified by gender, age at diagnosis and total dose of brain radiation.

To model the outcomes' pattern and change over time, we will use generalized estimating equation (GEE) methodology with time as the main independent variable while adjusting for gender, age at diagnosis and total dose of brain radiation, including an interaction term if indicated. The assigned distribution and link function in each model will depend on the characteristic of the specific outcome as listed in next paragraph(s). The continuous measures will be modeled using normal distribution and identity link whereas the binary outcomes will be modeled using binomial distribution and logit link.

These analyses will be conducted at the conclusion of the trial and at an interim time point at which we have 15 patients in each stratum (a total of at least 45 patients) followed for 1 year. The results of the interim analyses will be submitted for presentation at an appropriate national scientific meeting, as well as to the CT-SRC.

## List of outcomes:

Rev. 3.2 dated: 1/19/2023

Protocol document date: 1/19/2023

- 1. Overall physical performance: Two sets.
  - (a) Measured task sets: BOT2 (4-21 years old) and PPT (≥22 years old).
    - BOT2 outcome: total motor composite, a standardized score range from 20 to 80, with a mean of 50 and a standard deviation of 10.
    - PPT (7-item questionnaire) outcome: a score range from 0 to 28. The normative data is available from the human performance lab.

We will standardize the two above scores into z-scores for data analysis.

IRB APPROVAL DATE: 02/01/2023

- (b) Self-reported instruments (PROMIS): Three questionnaires.
  - Pediatric Physical Function Mobility SF1: 8-item questionnaire with the score range from 0 to 32.
  - Pediatric Physical Function Upper Extremity SF1: same as above.
  - Physical Function SF1: 10-item questionnaire with the score range from 0 to 50.

We will standardize the above scores into T-scores for data analysis based on the normative data from PROMIS.

- 2. Body Composition: BMI (kg/m2) and waist/hip ratio (cm/cm).
- 3. Flexibility
  - (a) Ankle dorsiflexion active and passive range of motion: measured by goniometer, and recorded as an angle (degree).
  - (b) Overall flexibility: measured by sit and reach test, and recorded as a length (cm).
- 4. Balance

Measured by sensory organization test (SOT), and the result from the test is the equilibrium score, a percentage range from 0% to 100%, with the higher percentage, the better balance. The outcome is a binary variable with a cutoff score of < 70% indicates future risk for a fall.

- 5. Coordination
  - (a) Fine motor coordination (finger and hand coordination).

    Measured by Composite Cerebellar Functional Severity Score (CCFS), and the outcome is an age-adjusted z-score and log transformed.
  - (b) Overall coordination

    Measure by brief ataxia rating scale (five-item questionnaire). The outcome is a total scale range from 0 to 22.
- 6. Muscle strength and power
  - (a) Lower extremity strength: measured by BiodexIII, and the outcomes are peak torque value/body weight ratios at different speeds of motion.
  - (b) Hand grip strength: measured by a Jamar hand held dynamometer and recorded in kilograms (kg).

We will standardize the above scores into z-scores for data analysis based on normative data.

7. Cardiopulmonary fitness

St. Jude Children's Research Hospital IRB NUMBER: Pro00004349 IRB APPROVAL DATE: 02/01/2023

- (a) Resting Energy Expenditure: measured with indirect calorimetry after an overnight fast and recorded as REE (kcal/day).
- (b) Cardiopulmonary Exercise test (CPET): the test will be completed on a treadmill using the Balke protocol or cycle ergometer using an incremental ramping protocol. The outcome is recorded as VO2max (ml/kg/min).

We will standardize the above scores into z-scores for data analysis based on normative data.

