Physical performance is dependent on the structural integrity and physiologic function of the nervous, musculoskeletal and cardiopulmonary systems, to provide a foundation upon which normal movement for everyday tasks can be accomplished. Movement created by the coordination of these three systems is also dependent on the health of the other body systems; that is, on intact skin to protect the body, on the gastrointestinal and urinary systems to process nutrients and body waste, and on the endocrine system to regulate metabolism. The general composition of the body is extremely important to movement as it governs the strength of the skeleton upon which movement occurs, the amount of lean muscle available to produce force, and the amount of body fat that must be carried while performing daily tasks. The structure and functions of the systems that govern movement are typically measured by assessing flexibility, balance, coordination, power, and cardiopulmonary fitness [89]. Lack of capacity can be defined for these measures. Impaired capacity in these systems is typically associated with overall physical performance limitations.

- 1. Flexibility is the capacity to bend and is based on the pliability of the muscles, connective tissue and skin, and on the ability of a joint to move through its range of motion. Girls are typically more flexible than boys [89, 92, 97].
- 2. Balance is the ability to maintain center of gravity over a base of support, thereby maintaining an upright posture either at rest or during movement [98]. Balance improves throughout childhood, is better in girls than boys during childhood, and plateaus in adolescence where young men's skill surpasses that of young women [99].
- 3. Coordination implies that the nervous and musculoskeletal system work together to produce smooth, efficient movement. It implies that the muscles work at the right time with the right intensity [100] to produce movement. Coordination is needed to get button or zip clothing, run, skip, and drive a car.
- 4. Power is the rate at which work is done and includes both muscle strength and speed of movement. It requires a muscle to develop tension and produce the force to move a body part through range of motion. Power increases during childhood and peaks during adolescence and young adulthood [101].

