#### 3.1 Inclusion Criteria

- Progressive intracranial ependymoma after prior focal irradiation
- Patients aged 1-21 years at the time of enrollment
- Adequate performance status (ECOG < 3) and research participant does not require mechanical ventilation
- Interval from start of initial radiation therapy to enrollment > 9 months

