## **Body Composition**

Anthropometric measurements, including height by wall mounted stadiometer (without shoes), weight by electronic scale, and waist and hip circumference, will be obtained. Trained clinic staff will measure waist and hip girths (cm) with a non-stretching anthropometric tape directly over the skin. Waist circumference will be measured midway between the anterior superior iliac spine, and the lower rib margin and hip girth will be measured at the maximum hip width. Measurements will be recorded to the nearest 0.5cm. Waist to hip ratio will be calculated by dividing waist by hip circumference. Intra- and inter-rater reliability coefficients are reported at 0.99 for waist and at 0.98 for hip measurements [248]. Waist circumferential measurements have a sensitivity of 85% to correctly classify persons with central adiposity when compared to classifications made by DEXA [249]. These measurements are part of the comprehensive evaluation and will not be treated as individual outcomes. Body weight and/or BMI are used to normalize strength values [250].

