## Balance

Balance will be measured by having the subject complete the sensory organization test (SOT) on a computerized dynamic posturography system (SmartEquitest, Neurocom International). Participants will stand on dual force plates which are pitched up or down in an anterior-posterior direction to provoke ankle motion. The participant stands in an upright position with the medial malleoli positioned directly over the axis of rotation of the force plates. A colored visual screen surrounds the participant on three sides. Visual and kinesthetic inputs are manipulated to create six different conditions, each of which is tested with three 20 second trials. During testing, the device continuously records the participant's center of pressure over the force plates. A difference score is computed from the normal range of anterior-posterior sway (12.5 degrees) and the maximum range of sway of the participant on each trial; that score is expressed as a percentage. The higher the score, the less the participant swayed. A trial ending in a fall (injury prevented because of the safety harness) is scored at zero [260]. Mean data from the three trials under each condition will be used to characterize balance. Reference data are available for typically developing children, adolescents and young adults from the literature and from normal population controls tested in our human performance laboratory [261-269].

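### Section 11.4 models balance with one 70% cut-off for all ages, and flexibility with no stated age reference, so its five-year time trend mixes normal development with change after re-irradiation

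*Combined protocol and SAP*

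**What the plan says.** Section 11.4 analyses physical performance by GEE "with time as the main independent variable while adjusting for gender, age at diagnosis and total dose of brain radiation", with an interaction if indicated. The schedule is: "Physical performance measures will be obtained at baseline, 12, 24, 36, 48 and 60 months". Section 3.1 sets the age range: "Patients aged 1-21 years at the time of enrollment".

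The list of outcomes in Section 11.4 treats the measures differently:

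- Item 1 (overall performance, PROMIS), item 6 (strength) and item 7 (cardiopulmonary fitness) each carry a sentence on conversion to z- or T-scores. Item 5(a) (fine motor coordination) is an age-adjusted z-score.
- Item 2 (BMI in kg/m2, waist/hip ratio), item 3 (ankle range in degrees, sit-and-reach in cm) and item 5(b) (ataxia total, 0 to 22) carry no such sentence.
- Item 4 (balance) is dichotomised: "The outcome is a binary variable with a cutoff score of < 70% indicates future risk for a fall".

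Elsewhere the protocol says of balance: "Balance improves throughout childhood, is better in girls than boys during childhood, and plateaus in adolescence" (Section 2.5). Section 6.8, Balance, adds: "Reference data are available for typically developing children, adolescents and young adults from the literature". Section 6.8, Flexibility, says the same of ankle range and sit-and-reach. Section 6.1 converts BMI to percentiles for age and gender. Section 6.8, Body Composition, says of the anthropometric measures: "These measurements are part of the comprehensive evaluation and will not be treated as individual outcomes".

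**The concern.** A child followed for five years grows up by five years. Age at diagnosis is one fixed number per child, so adjusting for it cannot remove ageing during follow-up, and no untreated group is followed alongside. Any outcome that changes with normal development, and is not referenced to age, carries that development into the time coefficient.

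For balance the protocol itself gives the direction: scores improve through childhood. A younger patient who loses balance relative to peers may still cross the 70% line upwards, or stay level. Section 2.5 says that this longitudinal assessment is meant to help weigh disease control against functional outcome, and Section 11.4 sends interim results to a national meeting. A trend that could be growth, loss or a sum of the two serves neither use well.

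**Working it through.** The plan gives no figure to reproduce here. The documents give no equilibrium-score means, SDs or growth rates, so every number below rests on stated assumptions and is shown as a range.

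**1. What the time coefficient estimates.** Let *g* be normal growth in a raw score per year of age and *d* the true change per year after re-irradiation. Age at assessment = age at diagnosis + interval to enrolment + time. The expected score is then a constant + *g* × (age at diagnosis + interval) + (*g* + *d*) × time. Adjusting for age at diagnosis absorbs only the between-child part. The coefficient of time is *g* + *d*.

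A simulation of the Section 11.4 model confirms this (identity link, exchangeable correlation, terms for time, sex, age at diagnosis and dose). It used 90 patients, six annual visits and 30 runs per cell, with assumed age at diagnosis 1 to 12 years, between-child SD 6 and within-child SD 5.

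| Growth *g* (points/yr) | True change *d* (points/yr) | Raw score: time coefficient | Score minus age norm: time coefficient |
|---|---|---|---|
| 0 | -1 | -1.02 | -1.02 |
| 1 | -1 | +0.02 | -0.98 |
| 2 | -1 | +1.00 | -1.00 |
| 2 | 0 | +1.99 | -0.01 |

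With the raw score, a loss of 1 point per year disappears at growth +1 and looks like a gain at growth +2. Scoring against the age norm recovers the true change at every growth rate tried, from 0 to 3.

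**2. The 70% cut-off.** Take a normally distributed score with baseline mean *m* and SD *s*, growth *g* per year, and a loss of *L* SDs by year 5 relative to the age norm:

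- share below 70 at baseline = Φ((70 - *m*)/*s*)
- share below 70 at year 5 = Φ((70 - (*m* + 5*g* - *L* *s*))/*s*)

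Example with *m* = 65, *s* = 8: baseline Φ(0.625) = 73%. At *g* = 2 and no loss, year 5 is Φ(-0.625) = 27%. With a loss of 0.5 SD (4 points), the year-5 mean is 65 + 10 - 4 = 71 and the share is Φ(-0.125) = 45%. With a loss of 1 SD it is Φ(0.375) = 65%. The share below 70 falls in all three cases, although two of them contain a real loss.

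Change in the share below 70 from baseline to year 5, in percentage points, for *m* = 60, 65, 70 and *s* = 8, 12:

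| Growth (points/yr) | No loss | Loss 0.5 SD | Loss 1 SD |
|---|---|---|---|
| 0 | 0 | +7 to +19 | +9 to +34 |
| 1 | -23 to -14 | -5 to +3 | +5 to +22 |
| 2 | -47 to -30 | -28 to -11 | -10 to +7 |
| 3 | -63 to -39 | -51 to -26 | -33 to -8 |

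A positive entry shows a worsening. At zero growth every loss is visible. At +1 a loss of 0.5 SD is nearly flat, while 1 SD still shows. At +2 a loss of 0.5 SD appears as an improvement.

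**The case against.** **Section 11.4 is descriptive.** Its objective is to describe performance. It specifies no treatment contrast and does not call the time coefficient an effect of re-irradiation. This stands: a reader might infer that the plan attributes growth to treatment, and the text does not say so. But it does model change over time, and a described trend still needs a known meaning.

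**The z-score sentence after item 6 refers loosely to the scores above it and might cover items 2 to 5.** This does not hold well. The sentence is repeated after item 7, which points to item-by-item use; a binary balance outcome cannot be a z-score; and fine motor coordination is already one.

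**BMI is dealt with elsewhere.** Largely true. A reader might infer that the whole protocol models raw BMI. It is raw in Section 11.4, but Section 6.1 plans percentiles and Section 6.8 says that these measures are not individual outcomes. What remains is a contradiction between Section 6.8 and item 2 of the list. BMI and waist/hip ratio are also not measures of function, so no loss of function is hidden there.

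**No direction is given for flexibility.** True. Section 2.5 reports only a sex difference, and gender is in the model. The lack of an age reference stands; the claim that it hides a loss would not.

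**The growth rates are assumed, and balance plateaus.** True. Patients may enrol up to age 21, and the masking vanishes at zero growth. Complete masking occurs only where loss and growth happen to match.

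**The plan has partial safeguards.** Descriptives stratified by age at diagnosis, individual profile plots and a possible interaction can show whether younger and older patients differ. They do not separate growth from loss within the younger group.

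**The 70% cut-off has its own meaning as absolute fall risk.** Agreed, and it should be kept as a description.

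**Conclusion.** The point holds for balance and flexibility. As written, the five-year time coefficient for these outcomes is the sum of normal development and change after re-irradiation, and neither age at diagnosis nor a control group separates them.

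For balance, a real loss in patients still developing can be partly or fully offset. For a loss of 0.5 SD the result ranges from no masking at zero growth, through a nearly flat share at +1 point per year, to an apparent improvement of 11 to 28 percentage points at +2. These sizes rest on assumed means of 60 to 70, SDs of 8 to 12 and a uniform growth rate. A cohort that includes patients past the plateau would show less.

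For flexibility, only the missing age reference is established. The documents do not support a claim that flexibility loss is hidden, that raw BMI is used throughout, or that the plan presents the trend as a treatment effect. This is a secondary objective; the primary analysis and the necrosis stopping rule do not depend on it.

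**What to change.** Amend Section 11.4 as follows:

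1. Add the continuous equilibrium score, standardised for age and sex with the reference data named in Section 6.8, Balance, as the modelled balance outcome. Keep the share below 70% beside it as a description of absolute fall risk.
2. Analyse ankle range and sit-and-reach as z-scores from the reference ranges named in Section 6.8, Flexibility.
3. If BMI is analysed, use the age and gender percentile already planned in Section 6.1.
4. Reconcile Section 6.8, Body Composition (not individual outcomes) with item 2 of the Section 11.4 list (an outcome).
5. Report the ataxia total (0 to 22) with the caveat that it is not referenced to age.
6. State, item by item, which scores are standardised.

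Adding age at assessment as a covariate is a weak substitute: within a child, age and time advance together, so growth is best removed with an external norm.

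The cost is SAP wording and some analysis work with reference data that the protocol already cites. Patients outside the age range of the norms would be reported descriptively. No new measurements are needed.
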